### **5.4. Loss to follow-up and missing data**

We will employ strategies we have used in prior studies to achieve excellent follow-up and minimal missing data. Because patients will require necessary postoperative and postpartum visits, there will be ample opportunity for follow-up. In addition, we will obtain two contact numbers from subjects when available and contact them on approximately postoperative day 30 ( $\pm 2$  days). We will also obtain written authorization to obtain records from their Emergency Room and physician office visits and hospital readmissions. We will employ active data management at each site, including monthly data review for rates and patterns of missing data. Remedial measures including re-abstraction of data and retraining of staff will be used as needed to minimize missing data. If data are still missing, we will address the deficiency analytically. We will first determine if data is missing at

random. We will then employ methods including multiple imputations and sensitivity analyses to test the robustness of our results.

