### **6.2.2. Secondary Analyses**

#### *Adjusted estimates*

We will perform analyses aimed at obtaining estimates of treatment effectiveness, adjusting for any imbalances in baseline subject characteristics between groups. The objectives of these analyses are to estimate the influence of covariates on the outcome and to use them to improve the estimated difference between treatment groups. Logistic regression models will be used to identify and estimate the effect of multiple prognostic factors on the probability of SSI and other categorical outcomes.

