Incremental cost per QALY:

$(\text{Mean Cost}_{\text{Prophylactic NPWT}} - \text{Mean Cost}_{\text{standard care}}) \div (\text{Mean QALY}_{\text{Prophylactic NPWT}} - \text{Mean QALY}_{\text{standard care}})$

All estimates of costs, outcomes, and cost-effectiveness will be reported as means with 95% confidence intervals. In accordance with the current threshold used in the U.S., prophylactic NPWT will be considered cost-effective if the incremental cost per QALY is less than \$100,000^62. We will conduct sensitivity analysis to evaluate uncertainty of the results by varying probability (e.g., baseline rate of SSI, magnitude of risk reduction) and cost parameters (e.g., cost of the NPWT device, healthcare cost). We will employ Monte Carlo simulation to assess the robustness of our findings by simultaneously sampling distributions of multiple parameters within the model.

*Etiology, timing, and risk factors of SSIs in obese women*

For these analyses, the two study groups (NPWT and standard care) will be combined into a cohort, and all analyses will adjust for group assignment and study site. We will evaluate wound culture data to determine the types and frequency of different bacteria including MRSA. We will use time-to-event analyses to estimate median time to SSIs and time to heal. We will identify risk factors

for SSI initially based on factors associated with SSI in bivariate analysis (at  $P<0.1$  threshold), biological plausibility, and factors reported in the literature. We will use backwards elimination to reduce the number of variables in the model. Variables that are significant will be retained as risk factors for SSIs in obese women. Fit for the final model will be assessed by using the Hosmer-Lemeshow goodness-of-fit test.

*Other planned secondary analysis*

- Effect of prophylactic negative pressure wound therapy on a composite of any wound complication
- Effect of prophylactic negative pressure wound therapy on rate and type of wound cultures
- Effect of prophylactic negative pressure wound therapy on healthcare resource utilization
- Association between levels of cefazolin in the subcutaneous layer before fascial incision and after fascial closure and risk of surgical site infection
- Risk of surgical site infection and other wound complications with different skin incision types
- Relationship between skin microbiome at the incision site and risk of surgical site infection

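### SSI risk factors are declared and reported only if significant in the same data that selected them, so weak-to-moderate factors will be overstated and intervals for the retained set will under-cover

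*Combined protocol and SAP*

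**What the plan says.** The procedure is in section 6.2.2, under the subheading on etiology, timing and risk factors of SSIs. The two arms are pooled into one cohort, and "all analyses will adjust for group assignment and study site". Candidates enter by three routes: they are "based on factors associated with SSI in bivariate analysis" (at P<0.1), or they come from "biological plausibility, and factors reported in the literature". Then "We will use backwards elimination to reduce the number of variables in the model", and "Variables that are significant will be retained as risk factors for SSIs in obese women". The check on the result is: "Fit for the final model will be assessed by using the Hosmer-Lemeshow goodness-of-fit test".

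The subsection does not name the effect measure. Logistic regression, and hence the odds ratio, follows from the Hosmer-Lemeshow test and from the adjusted-estimates paragraph of the same section: "Logistic regression models will be used to identify and estimate the effect of multiple prognostic factors on the probability of SSI".

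The plan gives no candidate list or number, no removal threshold, no significance level for this model, no internal validation or shrinkage, and no exploratory label. The robustness work elsewhere does not reach this model. Section 5.4 deals with missing data ("We will then employ methods including multiple imputations and sensitivity analyses to test the robustness of our results"), and the sensitivity analyses and Monte Carlo simulation in section 6.2.2 belong to the economic evaluation.

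**The concern.** The same SSI outcomes choose the variables, decide which are called risk factors, and supply the estimates and intervals. A variable reaches the list only if its estimate is far enough from the null to be significant, so the reported estimates are a filtered sample, and the usual intervals take no account of the filter. Hosmer-Lemeshow compares observed with predicted risk in the data used for fitting. It cannot show that a variable was kept by chance or that its effect is too large.

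At stake is the product of this analysis: a named list of risk factors for SSI in obese women, which readers may use for counselling, risk scores or later trial design. Weak real factors would mostly be missing from it, those present would look stronger than they are, and some entries could be chance findings.

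**Working it through.** **1. Events available.** The plan's sample size comes first, because it fixes the number of events. Inputs from section 6.1.1 and Table 4: 10% vs 7%, two-sided 5%, 80% power, 5% loss.

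n per arm = [1.96·√(2·0.085·0.915) + 0.8416·√(0.10·0.90 + 0.07·0.93)]² / 0.03² = 1356, so 2712 in total. Allowing for loss gives 2712/0.95 = 2855 or 2712·1.05 = 2848, so the plan's 2850 is reproduced. Expected SSIs: 2850·0.95 ≈ 2708 women, and 2708·0.085 ≈ 230 events.

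**2. Assumptions.** The documents give neither the number of candidates nor the final threshold. I use 10 to 30 candidates and P<0.05. The simulations used 2708 women, the P<0.1 screen and then backward elimination; the runs in the table in step 4 also forced in arm and five sites.

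**3. Why kept factors are overstated.** Take a binary factor with 20% prevalence (assumed). Approximately, SE(log OR) = 1/√(2708·0.085·0.915·0.20·0.80) = 1/√33.7 = 0.172. To be significant in the harmful direction the estimate must exceed exp(1.96·0.172) = 1.40. A true odds ratio of 1.3 therefore cannot be reported correctly if it is kept. It is kept with probability about Φ[(ln 1.3 − 0.338)/0.172] = Φ(−0.44) ≈ 33%.

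**4. Simulation, 5 real factors (20% prevalence) and 15 noise candidates, 400 replicates per row.**

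| True OR | Kept | Mean OR when kept | Coverage, real factors kept | False factors per model | Coverage, whole list |
|---|---|---|---|---|---|
| 1.2 | 19% | 1.50 | 85% | 0.73 | 48% |
| 1.3 | 37% | 1.53 | 91% | 0.76 | 65% |
| 1.5 | 73% | 1.61 | 96% | 0.77 | 79% |
| 2.0 | 99% | 2.00 | 95% | 0.67 | 84% |

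A false factor kept at P<0.05 has an interval that excludes 1 by construction, so its coverage is zero. The last column is (5 × kept × coverage)/(5 × kept + false factors). For 1.3: 5·0.37·0.91/(5·0.37 + 0.76) = 1.68/2.61 ≈ 65%.

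With 25 candidates of which 8 are real, coverage of the retained set is about 82%; with 12 of which 8 are real, about 92%. Across the runs, a factor with true OR 1.3 was kept in about 33-46% of trials, with a mean of about 1.5 when kept.

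**5. Chance of at least one false factor.** With k null candidates each tested at 5%, it is 1 − 0.95^k.

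| Candidates | Null (k) | Formula | Simulated |
|---|---|---|---|
| 12, 8 real | 4 | 18% | 16-18% |
| 10, none real | 10 | 40% | 40% |
| 25, 8 real | 17 | 58% | 52-61% |
| 20, none real | 20 | 64% | 61% |
| 25, none real | 25 | 72% | 72-76% |
| 30, none real | 30 | 79% | 78% |

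The formula contains no screening or elimination step, yet it matches. With a final threshold of 0.10 and 20 null candidates, the simulated figure is 86%.

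**6. Which step does the damage?** With 25 candidates (8 real), screening plus elimination left at least one false factor in 61% of models. A single full model read at P<0.05 did so in 65%. Coverage of the significant variables was 82% under both. In a second run of that design, the mean estimate for a true OR of 1.3 was 1.485 after elimination and 1.49 in the full model, with 46% kept under each. Entering 20 null candidates directly, without the bivariate screen, gave 65%.

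**The case against.** A reader might infer that the bivariate screen and backward elimination themselves generate false factors, and that a full model would cure this. Steps 5 and 6 do not support that. The false-factor rate is ordinary multiplicity, and a full model read at P<0.05 has as much of it. It would likewise mislead to set about 82% coverage for retained variables against 95% for all variables in a full model, since these are different sets. For significant variables only, the two approaches agree. What stands is narrower: the harm comes from declaring and reporting only what is significant.

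A reader might also infer that false factors are likely. That depends on a candidate number the documents do not give. With 12 candidates, 8 of them real, the chance is about 16%; with 10 pure-noise candidates it is 40%.

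The plausibility and literature routes are a fair point in the plan's favour. They can raise the share of real factors among the candidates, and strong factors (odds ratio near 2.0) are estimated well. But variables entering by those routes still meet the same elimination and the same significance rule.

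The stakes are limited too. This analysis is not among the specific aims, the research questions or the listed outcomes. Section 5.3 says the analysis plan is still to be finalized by the steering committee, with DSMB approval, so thresholds and a list could be added there. That is a reason to settle the matter then, not a reason to leave the rule as written.

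**Conclusion.** The concern holds as a minor point about a secondary analysis. Followed as written, the plan gives a list in which weak-to-moderate factors are overstated when kept and intervals under-cover, by an amount that depends mainly on how many candidates are null. Factors with an odds ratio near 2.0 are not materially inflated, although coverage over the whole list can still fall short (84% in step 4) because of false entries.

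The size rests on about 230 events at the planned rates, a 5% final threshold, and assumed numbers, prevalences and effects of candidates. The direction of the bias does not depend on those choices. The comparison of NPWT with standard dressing and its type I error are not touched.

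**What to change.** Replace the screen, the elimination and the rule that keeps only significant variables with the following.

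- Fix the candidate list from the literature and plausibility before SSI outcomes are examined. The time that matters is before outcome data are seen, not before arms are unblinded, because the arms are pooled and selection is on SSI.
- Size the list to about 230 events, counting the forced terms. Arm (1), five sites (4), BMI category (1) and cesarean stratum (1) take 7 parameters. A total of about 20 gives 230/20 = 11.5 events per parameter and leaves about 13 for candidates.
- Fit one full model and report every factor with its 95% CI, whatever its P value. In simulation this restores coverage to about 95%.
- Label the analysis exploratory and do not declare risk factors by P<0.05. The full model does not itself control multiplicity, so some intervals may exclude 1 by chance.
- If a shorter model is wanted, report bootstrap inclusion frequencies and an optimism correction that repeats every selection step.

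The cost is a change of wording in section 6.2.2 and modest extra analysis, with no new data. The downside is a longer table and wider intervals.

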## **7. Safety monitoring**

The interventions compared in this trial are both currently used in clinical obstetric practice. Further, the adverse events reported with use of prophylactic NPWT at cesarean were minor and their frequency was comparable to rates with standard dressing. Therefore, no serious or life-threatening adverse events are expected in this trial. Nonetheless, the following measures will be taken to monitor and investigate adverse events:

### **7.1. Independent Data and Safety Monitoring Board (DSMB)**

An independent study-specific DSMB will be composed of three distinguished individuals ([name], MSCE; [name], MSCI; and [name]) who represent appropriate expertise in epidemiology, obstetrics, clinical trials, and biostatistics. They will provide oversight to assure that the trial accrues at a sufficient rate and that the safety and privacy of all study participants is assured. The DSMB will hold conference calls every six months to review study progress and monitor adverse events.

### **7.2. Adverse events reporting**

#### *Reportable Events*

Each site-PI will oversee the safety of the study at his/her site. During the study, the investigator or study site personnel will be responsible for querying and recording adverse events (AEs) and serious adverse events (SAEs), as detailed below.

*Types of Reportable Events:*

*Serious Adverse Events (SAE)*

The site must report all SAEs to the lead site, whether or not they result from study participation, within 24 hours of learning of the event. A serious adverse event (SAE) is any adverse event occurring within the timelines specified in the protocol that results in any of the following outcomes:

- Death
- Life-threatening situations (subject is at immediate risk of death)
  - Postpartum hysterectomy for infection control
  - Maternal sepsis
  - Necrotizing fasciitis
  - Maternal ICU admission

*Adverse Events (AE)*

An adverse event is any untoward medical occurrence in a clinical investigation subject administered an investigational product and which does not necessarily have to have a causal relationship with this treatment. An AE can, therefore, be any unfavorable and unintended sign (that could include a clinically significant abnormal laboratory finding), symptom, or disease temporally associated with the use of a medicinal product, whether or not considered related to the medicinal product.

For this study, abnormal laboratory findings (e.g., clinical chemistry, hematology) or other abnormal assessments (e.g., electrocardiogram, X-rays, vital signs) per se are not reported as AEs. Only the Adverse Events of Special Interest (AESI) defined below will be recorded on the CRFs and in the subject's chart.

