#### **4.6. Follow Up**

- We will use active surveillance by research staff to ascertain surgical site infections.
- Research staff will follow-up with the research participant on the day of discharge or within 48 hours (postpartum day 2-7) to assess for adverse events, assess the participant's pain and obtain their satisfaction with their dressing.
- Research staff will call subjects on approximately postoperative day 30 ( $\pm 2$  days). They will ask the patient standardized questions regarding wound complications. If the patient reports a hospital, clinic, or ER visit not associated with the study centers, the staff will obtain the name of the medical facility and request the records.
- The EQ-5D-3L quality of life questionnaire will be administered at the 30-day call.
- Typically, patients will have routine follow-up with their provider scheduled at 1-2 weeks and 4-6 weeks post-partum.
- We will obtain medical records from each of those clinic visits as well as records of unscheduled visits (to any hospital clinic or ER) to ascertain study outcomes

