#### **4.8.2. Secondary Outcomes**

[figure not shown]
- Individual components of the primary outcome (superficial or deep SSI)
- Organ space SSI (endometritis)
- Other individual wound complications: dehiscence  $\geq 2$  cm, hematoma, seroma, erythema

- Composite of any wound complications
- Patient pain and satisfaction scores at discharge and postoperative day 30
- Patient satisfaction with aesthetic appearance (scale of 0 - 10) at postoperative day 30
- Healthcare resource utilization: physician office or ED visits, antibiotics for SSI, hospital readmission for SSIs, home health for SSI, wound clinic for SSI
- Adverse events: skin blistering, allergic reaction, wound bleeding

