## *Adverse Events of Specific Interest (AESI)*

Adverse events of particular clinical importance (other than SAEs mentioned above) will be classified as adverse events of specific interest (AESIs). For this study, AESIs refer to:

- Mild/moderate reactions:

- Skin blisters
- Wound bleeding
- Allergic skin reaction

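### A readmission or reoperation for a non-infectious wound event that is not life-threatening and does not reach the ICU is neither an SAE nor a named readmission outcome, so the readmission outcome is one-sided for the safety aim

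*Combined protocol and SAP*

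**What the plan says.** Section 7.2 (Reportable Events) defines an SAE as an adverse event "that results in any of the following outcomes", and two follow: death and "Life-threatening situations (subject is at immediate risk of death"). Beneath the second stand four items: "Postpartum hysterectomy for infection control", sepsis, necrotizing fasciitis and "Maternal ICU admission". SAEs must be reported within 24 hours.

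Below that level, "Only the Adverse Events of Special Interest (AESI) defined below will be recorded on the CRFs". There are three of these AESIs: skin blisters, wound bleeding and allergic skin reaction, under the heading "Mild/moderate reactions". Each adverse event report records severity, relationship to treatment, action taken and outcome. AESIs that are not severe go to the lead site in aggregate every six months.

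Section 4.8.2 lists hematoma, seroma, erythema and dehiscence of at least 2 cm as secondary outcomes, plus a composite of any wound complication. Under resource use it names office and emergency visits without a stated cause, but readmission only as "hospital readmission for SSIs".

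For source data, section 4.6 obtains "records of unscheduled visits (to any hospital clinic or ER) to ascertain study outcomes". Section 5.4 adds written authorization for readmission records, with no restriction on cause.

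**The concern.** Safety is Secondary Aim 1, and the protocol itself treats bleeding as a device concern. Section 3.3.2 lists bleeding disorder and therapeutic anticoagulation among the contraindications to the device, and section 9 names wound bleeding as a potential risk. The events one would want to compare between arms include bleeds, hematomas and dehiscences bad enough to bring a woman back to hospital or to theatre, even when her life is not in danger. As written, the SAE definition does not reach them, and the readmission outcome is confined to the cause that the device is intended to reduce. A readmission comparison could then favour the device because readmissions for other wound causes fall outside it.

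**Working it through.** No stated figure is in dispute, so the check is to follow each kind of event through the definitions. In the first three rows the event is non-infectious, carries no immediate risk of death and involves no ICU stay.

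| Event | SAE (7.2)? | Adverse event report required (7.2)? | Wound event counted (4.8.2)? | Readmission or reoperation counted (4.8.2)? |
|---|---|---|---|---|
| Hematoma, readmitted for evacuation | No | No, not an AESI | Yes | No |
| Dehiscence of at least 2 cm, readmitted or re-sutured in theatre | No | No, not an AESI | Yes | No |
| Wound bleeding, readmitted | No | Yes, AESI | Yes, as an adverse event outcome | No |
| SSI, readmitted | Only if a listed condition applies | No, unless an SAE | Yes | Readmission yes |
| Any of these with ICU admission | Yes | Yes | Yes | Only if SSI |

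Four steps support the table.

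1. **The SAE list is closed.** An event must result in a listed outcome. The only procedure listed is hysterectomy, and only for infection; the only admission is to the ICU. The layout leaves open whether the four items are examples of a life-threatening situation or criteria of their own. Neither reading adds ordinary readmission or reoperation.

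2. **The AESI tier catches only bleeding.** Hematoma and dehiscence are not AESIs, so the severity and action-taken fields need not be completed for them. In the outcome data, a small hematoma left alone and one evacuated in theatre count the same.

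3. **The routes do not meet.** Section 7.2 sends SAEs within 24 hours and non-severe AESIs every six months. Its severity table accepts that a severe event may fall short of an SAE. A severe wound bleed that is not an SAE therefore has no stated route.

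4. **No other outcome fills the gap.** Reoperation is not a named outcome; it appears only within the deep SSI definition in section 4.8.1, as one way of finding an abscess.

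The safety power statement in section 6.1.2 does not help here. It concerns composite adverse events, 16% against 12%. It reproduces with the usual two-proportion formula: 86.8% power at 1425 per arm, and 85.1% at 1353 per arm (1425 × 0.95, rounded down), against the stated 85%. It gives no assurance about readmissions or reoperations, for which the documents state no rate.

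**The case against.** A reader might infer that these events disappear, or that the DSMB would see only life-threatening events and trivial reactions. The documents do not support that. Wound bleeding is an AESI, its report records severity, action taken and supporting records, and the severity scale has a severe grade between moderate and life-threatening. Hematoma and dehiscence are compared between arms as outcomes. Office and emergency visits are not limited to SSI, section 6.2.2 plans an analysis of resource use, and the cost analysis includes treatment of side effects. What is missing is narrower: the readmission or reoperation as a counted event, and a reporting route for it.

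Some of these wounds may also be classed as SSI. Under section 4.8.1, a deep incision that dehisces or is opened by a surgeon, is not cultured, and is accompanied by fever or local pain can meet a deep SSI criterion; a superficial criterion works similarly. The definition also requires infection, so central review may exclude some. The gap is smaller to that extent.

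A reader might also want a count of the events missed. That would rest wholly on an assumed rate.

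Finally, this is a pragmatic trial of two dressings in current use, section 7 expects no serious events, and a tailored SAE list is a legitimate choice. The Manual of Operations and data collection forms, which are not among the documents, may already record readmission for any cause. Both points lower the urgency. Neither removes the gap: an expectation of no serious events is something the safety data should be able to test, and a field on a form is not an outcome until the protocol names it.

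**Conclusion.** The point holds in limited form. Followed as written, the plan does not count a readmission or reoperation for a non-infectious wound event below the life-threatening or ICU threshold, either as an SAE or as a readmission outcome. It requires no adverse event report when the event is a hematoma or dehiscence, and it states no route for a severe AESI that is not an SAE. The readmission outcome is one-sided for the safety aim. The primary outcome, its analysis and the sample size are untouched.

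The number of events affected cannot be estimated from the documents, and the conclusion does not depend on it. It rests on reading the SAE list as closed, which its wording supports, and on the protocol text alone. This is an inexpensive improvement that should be made; it does not threaten the trial's main conclusion.

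**What to change.** - **Section 4.8.2:** replace the SSI-only readmission item with readmission or reoperation for any wound-related or dressing-related cause, reported by arm, with the SSI subset shown separately. The total then does not depend on how a reopened wound is classified.
- **Section 7.2, serious events:** add inpatient readmission or return to the operating room for a wound-related or dressing-related event other than a protocol-defined SSI. Keep SSI readmissions as outcome data unless they meet an existing SAE criterion. The rule that every SAE is reported within 24 hours then needs no exception.
- **Section 7.2, routes:** state how and when a severe AESI that is not an SAE is reported, and reconcile this with the mild/moderate heading over the AESI list.

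The cost is a wording amendment and, if the forms lack it, a field for the reason for readmission or reoperation. The records are already sought under sections 4.6, 5.4 and 7.2. The downside is a modest rise in SAE reports. The change concerns reporting definitions only, not patient care.

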*Chaboyer et al* recently published a pilot randomized trial in which 87 obese women undergoing elective cesarean were randomized to prophylactic NPWT or standard dressing. Use of prophylactic NPWT was associated with a statistically non-significant 19% decrease in SSI (22.7% vs 27.9%; RR 0.81, 95% CI 0.38-1.68). The authors also found no differences in the frequencies of adverse events (7/44 [15.9%] with NPWT vs 7/43 [16.3%] with standard dressing), and all were minor (skin blisters, erythema, bruising, and wound bleeding). Although more methodologically sound than the others, this

study was limited by including only elective cesareans, the small sample size and differences in prognostic baseline characteristics between the two groups.

Taken together, these studies suggest a 65% decrease in SSIs after cesarean with prophylactic NPWT (random effects model: pooled RR 0.35, 95% CI 0.12-1.04). Although results of these studies are promising, the small sample sizes, between-study heterogeneity, and methodological limitations preclude definitive conclusions on the effectiveness of prophylactic NPWT in obese women after cesarean.

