## **2.2. Adverse Effects of Prophylactic NPWT**

The Single Use Prophylactic Negative Pressure Wound Therapy System received FDA marketing approval in 2012. As of September 2015, we identified two reports on the FDA website of blistering at the site of application from the PICO device. A third report of a minor burn from the PICO pump device occurred in a patient after neurosurgery while still unconscious. The patient was found to have been lying on the pump device for a prolonged period of time.

A high rate of skin blisters was reported when NPWT was used after orthopedic surgery, but not with other surgical procedures. This was attributed to use of the adhesive dressing in the setting of marked swelling and edema. Case series suggest approximately 10-15% rate of skin irritation and blisters at the device application site. The majority (~90%) did not require treatment beyond removal of the device. Moreover, adverse events noted with NPWT after cesarean were minor and comparable in frequency to standard dressing.

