#### **6.1.2. Secondary Aim 1 - Safety**

The sample size of 2,850 subjects for the primary aim will be sufficient to detect at least a 25% difference in composite adverse events between the two groups with 85% power and significance

level of 5%. This represents the difference between a 16% rate of composite adverse events with NPWT (based on preliminary data) and 12% with standard dressing.

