## *Data Monitoring and Quality Control*

Periodic monitoring visits will be made at the investigational site throughout the clinical study to ensure that the investigator obligations are fulfilled, and all applicable regulations and guidelines are being followed. These visits will ensure that the facilities remain acceptable, the investigational plan is being followed, the IRB and local authorities have been notified of approved investigational plan changes as required, complete records are being maintained, appropriate and timely reports have been made to the sponsor and/or its designees and the IRB, and the investigator is carrying out all agreed upon activities.

An annual report will be generated beginning one year after the first enrollment and will include the following:

- A list and summary of adverse events;
- Whether adverse event rates are consistent with pre-study assumptions;
- A summary of recruitment and retention and reason for dropouts;
- Whether the study is on track to be completed and accomplish the stated aims.

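### Apart from serious events, the trial records only skin blisters, wound bleeding and allergic reaction, so skin irritation, bruising and pump injury, which the protocol itself describes with NPWT, are not captured for the safety aim

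*Combined protocol and SAP*

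**What the plan says.** Section 7.2 (Reportable Events) first defines an adverse event broadly, as any untoward occurrence, and then narrows what is kept: "Only the Adverse Events of Special Interest (AESI) defined below will be recorded on the CRFs and in the subject's chart". The next heading defines that group: "Adverse events of particular clinical importance (other than SAEs mentioned above) will be classified as adverse events of specific interest (AESIs". Three items follow, skin blisters, wound bleeding and allergic skin reaction, with no category for other events. Section 4.8.2 has the same three: "Adverse events: skin blistering, allergic reaction, wound bleeding". Serious adverse events are reported separately and are limited to death and life-threatening situations.

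The background describes more than these three. Section 2.2: "Case series suggest approximately 10-15% rate of skin irritation and blisters at the device application site". The same section adds: "A third report of a minor burn from the PICO pump device occurred in a patient after neurosurgery while still unconscious". On the pilot randomized trial in elective cesarean, section 2.1.3 (Obstetric Patients) says of the adverse events that "all were minor (skin blisters, erythema, bruising, and wound bleeding").

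Section 6.1.2 plans the safety comparison on a "16% rate of composite adverse events with NPWT" against 12% with standard dressing, and states 85% power. The annual report in section 7.2 (Data Monitoring and Quality Control) is to consider "Whether adverse event rates are consistent with pre-study assumptions".

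**The concern.** Safety is a named aim of the trial. Section 1.2 words Secondary Aim 1 as an open list of adverse events that includes the three, but the recording rule makes the list closed. The rule is thus narrower than the aim it serves, and narrower than the harms that the protocol cites as its reason for looking.

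The restriction also sits badly with the rest of section 7.2. Each report must say whether the event was expected, yet an unlisted non-serious event produces no report. The severity table allows that a severe event may fall short of serious, yet a severe event outside the three has no place to go. The DSMB, which monitors adverse events every six months, would inherit the gap. Because the rule covers the subject's chart as well as the case report forms, later retrieval of these events could not be relied on.

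**Working it through.** **1. Named events against the places where they could be recorded**

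| Event named in the background | Source | Adverse event list (4.8.2, 7.2) | Serious event list (7.2) | Other outcome (4.8.2) |
|---|---|---|---|---|
| Skin blisters | 2.1.3, 2.2 | yes | no | no |
| Wound bleeding | 2.1.3 | yes | no | no |
| Erythema | 2.1.3 | no | no | yes, wound complication |
| Skin irritation, non-allergic | 2.2 | no | no | no |
| Bruising | 2.1.3 | no | no | no (hematoma is listed) |
| Pump burn, not life-threatening | 2.2 | no | no | no |

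Some irritation might be coded as an allergic reaction, and a large bruise as a hematoma, but no rule says so.

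**2. How large the gap could be**

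The only rate given is 10-15% for irritation and blisters together. Assume that it applies to the 1425 women in the NPWT arm: 0.10 × 1425 = 142.5 and 0.15 × 1425 = 213.75, so about 143 to 214 women with one or the other. The blister part would be recorded and the irritation part would not. The split is not given, so the missed number could lie anywhere from near zero to most of that total.

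**3. The plan's own power figure**

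Inputs: 16% and 12% (6.1.2), two-sided 5% level (6.1.1), 1425 per arm less 5% loss = 1353.75, taken as n = 1354.

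Power = Φ[(d − 1.96·s0)/s1], where d = p1 − p2, p̄ is the mean of the two rates, s0 = √(2·p̄(1 − p̄)/n) and s1 = √([p1(1 − p1) + p2(1 − p2)]/n).

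With p̄ = 0.14: s0 = 0.01334, s1 = 0.01331, and (0.04 − 0.02614)/0.01331 = 1.04. Power is 85.1%. With 1425 per arm it is 86.8%. The stated 85% reproduces.

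**4. Does the 16% describe the three-event composite?**

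The only adverse event rate in the documents that fits is the pilot's NPWT arm: 7/44 = 15.9%. The pilot's listed events were blisters, erythema, bruising and wound bleeding. The trial's are blisters, wound bleeding and allergic reaction. The two sets share two items, and each has something that the other lacks, so neither contains the other. Two facts weaken the link. Reference 58, cited for the 16%, is about patient-safety research and electronic health records. And the pilot's control rate was 7/43 = 16.3%, not 12%.

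**5. What if the three-event rate were lower?**

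The documents give no such rate, so the following rests on assumed rates only, with 1354 per arm.

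| Assumption about the removed events | NPWT vs standard | Power |
|---|---|---|
| One quarter of events removed in each arm, 25% relative difference kept | 12% vs 9% | 72% |
| One half removed in each arm, 25% relative difference kept | 8% vs 6% | 53% |
| Same 4 points removed from each arm | 12% vs 8% | 93% |
| Same 8 points removed from each arm | 8% vs 4% | 99% |

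The sign of the change depends on whether the removed events differ between arms, which the documents do not say.

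**The case against.** Targeted collection of adverse events is a defensible choice in a pragmatic trial of an FDA-cleared device. By section 2.2, about 90% of the case-series skin events needed nothing beyond removing the device. The burn was a single minor one, with a different brand, in an unconscious neurosurgical patient lying on the pump. Erythema and hematoma are already compared by arm, and a composite of wound complications is planned. The day-30 call asks about wound complications, and pain and satisfaction with the dressing are collected. The Manual of Operations and the forms, which are not part of the documents, may hold more fields. Randomized concurrent controls and the DSMB protect the comparison more than any historical benchmark does.

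Much of this stands, and it limits the weight of the point. It does not close the gap. Irritation without an allergic label, bruising short of a hematoma, and pump injury remain unlisted, and section 7.2 as written leaves no room for extra fields on the forms.

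Three stronger readings are tempting, and the documents do not support them.
- A reader might infer that the commonest device harm is left out. Section 2.2 gives irritation and blisters as one figure, so their order is unknown.
- A reader might infer that 85% power is wrong for the recorded composite. It reproduces on its inputs, and under assumed narrower rates power can fall or rise.
- A reader might infer that the annual check is biased towards reassurance. The check is not tied to the 16%, the source of the 16% cannot be confirmed, and whether the three-event rate lies below 16% is unknown.

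**Conclusion.** The point holds as a gap in safety recording. Apart from serious events, three event types are kept, while non-allergic skin irritation, bruising and non-life-threatening pump injury are described in the background and listed nowhere. Secondary Aim 1 would be answered without them, and for erythema only under another label. The omitted events are mostly minor, so this is a change that should be made rather than a flaw that threatens the trial. The conclusion rests on the text of sections 4.8.2 and 7.2 and assumes that the forms follow it.

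The benchmark is a conditional point. The 16% resembles the pilot's 15.9%, which counted a different and overlapping set of events, but this is an inference from a matching figure. What can be asked for is a definition. No error in the power calculation, loss of power or direction of bias is shown.

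**What to change.** 1. In sections 4.8.2 and 7.2, add to the adverse event list and to the existing AE/SAE form, in both arms: non-allergic skin irritation or erythema under or at the border of the dressing; bruising; and burn or pressure injury from the pump or tubing. Amend the sentence in section 7.2 that restricts recording, and bring section 1.2 into line.
2. Report the wider composite and the present three-event composite side by side, by arm.
3. In section 6.1.2, state which event definition the 16% and 12% describe, and correct the reference. Use the composite with the matching definition for the power statement and for any annual check against those rates.

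The cost is a few tick boxes on a form that is already completed at four time points, plus a wording amendment. The drawback is that minor irritation and erythema are common and partly subjective, so the wider composite will be noisier. Keeping the three-event composite beside it deals with that. Events not recorded before the change may not be recoverable, so an early amendment is worth more than a late one.
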